#### 7.4. PREMATURE STUDY TERMINATION

The study will be prematurely terminated in any of the following cases:

- Recurring serious or severe ADR (defined in Section 9.1) clinically evaluated by PI and/or Sponsor as warranting study termination.
- A decision made by Sponsor and/or IRB/EC and/or local regulatory agency to terminate the study.

#### 7.5. DEVIATION FROM STUDY PROTOCOL

The investigator shall not deviate from the study protocol without first obtaining a written approval from the Sponsor, or its official designee, and if applicable, from the local IRB/EC according to local regulations.

In the event of medical emergencies, the investigator shall use appropriate medical judgment and will remove the subject from any immediate hazard, then notify the Sponsor or its official designee and if applicable, the local IRB/EC, within 2 days, of the type of emergency and course of action taken.

Any other changes to or deviations from the protocol will be made as an amendment to the protocol and must be approved by the Sponsor or its official designee and the local IRB/EC before they can be implemented. Accordingly, the Sponsor will not assume responsibility or liability for any unauthorized deviation from or change to the protocol.

#### 8. INVESTIGATIONAL PRODUCT AND VEHICLE SPECIFICATIONS

#### 8.1. DESCRIPTION OF RZL-012

RZL-012 investigational drug is intended for a single dose in multiple injections into the subcutaneous fat. The injection dosing regimen and technique is crucial for the therapy safety and efficacy.

### 8.2. FORMULATION, PACKAGING AND LABELING

The RZL-012 drug is a ready to use liquid to be injected to the subcutaneous fat, supplied in a 1 vial kit. 1 vial contains 250 mg/4.8 mL RZL-012 in formulation F12.

The vehicle is a ready to use liquid to be injected to the subcutaneous fat, supplied in a 1 vial kit. 1 vial contains 1 mL of formulation F12.

#### 8.3. STORAGE AND STABILITY OF RZL-012 AND VEHICLE

The RZL-012 and vehicle kits will be stored in the site pharmacy at monitored room temperature conditions ( $22 \pm 7$  °C) protected from light. Storage space will be separate, designated and adequately labeled as containing investigational product.

Stability program of RZL-012 is ongoing and site inventory will be managed by the Sponsor according to accumulating stability data. Suitability of the product's expiration date must take into consideration and comply with FIFO (First In First Out) principals.

The storage conditions are summarized in Table 3.

Table 3: RZL-012 and Vehicle Storage Conditions

Storage Conditions	Maximal Storage Duration							
Individual vials:	According to expiration date as will be							
Room temperature (15-30 °C)	provided by manufacturer.							
* Stability program for RZL-012 is ongoing and site inventory will be managed by the								
Sponsor according to accumulating stability data.								

### 8.4. DOSAGE, DISPENSING AND ADMINISTRATION OF RZL-012 AND VEHICLE

### **8.4.1.** Dosage

RZL-012 therapy is available in vials of 250 mg/4.8 mL.

The vehicle is available in vials of 4.8 mL.

#### 8.4.2. Administration and Instructions for Use

Each individual vial must be kept and handled at room temperature.

The vial should be manually shaken before consumption.

1 mL Luer-lock syringes with RZL-012 solution should be filled with 30 G 1/2" sterile needle as described below:

- Cohort 1: 8 x 0.1 mL/syringe/subject
- Cohort 2: 16 x 0.1 mL/syringe/subject
- Cohort 3: 24 x 0.1 mL/syringe/subject
- Cohort 4: 36 x 0.1 mL/syringe/subject

One vial may be used for dosing of two subjects that are dosed together. Dosing of both subjects will be within a maximum of 4 hours. If only one subject is to be dosed, a single vial will be administered to that subject. Breached vials will not be re-used for other subjects. Each vial must be placed back into the container. All open vials must be kept until the end of the study for the Sponsor to decide either to discard or return to the Sponsor.

#### 8.5. ACCOUNTABILITY OF RZL-012 AND VEHICLE

The RZL-012 investigational product was manufactured by PharmaCore (USA) and complies with cGMP requirements. Formulation and packing was done by Nextar (Israel) and complies with cGMP requirements.

The vehicle was manufactured and packed by FusionRx (USA) and complies with cGMP requirements.

The RZL-012 investigational product and vehicle will be supplied in kits, in quantities as needed to comply with the treatment of site subjects according to the study protocol.

Site coordinator will notify the Sponsor or its official designee, in a timely manner and no less than 14 working days in advance, of any supply requirements to prevent shortage.

Shipment, storage and inventory documentation will be updated regularly and kept in the investigation files at the site to allow inspection and trace of the supplied product.

#### 9. ADVERSE EVENTS

#### 9.1. ADVERSE EVENT DEFINITIONS

#### 9.1.1. Definition of Adverse Event (AE)

An AE is defined as any untoward medical occurrence in a clinical investigation subject administered a pharmaceutical product and which does not necessarily have to have a causal relationship with this treatment. An AE can therefore be any unfavorable and unintended sign (including an abnormal laboratory finding, for example), symptom, or disease temporally associated with the use of a medicinal product, whether or not considered related to the medicinal product. This definition includes any abnormalities or anomalies that were not seen at baseline or which worsened during the course of the study, if present at baseline.

#### 9.1.2. Definition of Serious Adverse Event

A SAE is defined as any AE occurring at any dose that results in any of the following outcomes:

- death
- a life-threatening AE, as defined below
- subject hospitalization or prolongation of existing hospitalization
- a persistent or significant disability/incapacity
- a congenital anomaly/birth defect
- important medical event, as defined below

A life-threatening AE is any AE that places the subject, in the view of the investigator, at immediate risk of death from the reaction as it occurred (i.e., it does not include a reaction that, had it occurred in a more severe form, might have caused death).

An important medical event is an AE that may not result in death, be life-threatening, or require hospitalization but may be considered a serious AE when, based upon appropriate medical judgment, may jeopardize the subject and may require medical or surgical intervention to prevent one of the outcomes listed above. It can also include AEs otherwise judged to be serious by either the investigator or the Sponsor.

### 9.1.3. Definition of Adverse Drug Reaction

AEs associated with the use of investigational product (i.e., probably or possibly related to treatment as defined in Section 9.3) are also termed Adverse Drug Reactions (ADRs).

#### 9.2. ADVERSE EVENT GRADING

AE will be documented and graded according to the National Cancer Institute Common Terminology Criteria for Adverse Events (CTCAE) v4.03 June 14, 2010) (10).

AE that do not appear in the CTCAE will be graded as follows:

- Mild (Grade 1): Sign or symptom, usually transient, requiring no special treatment and generally not interfering with usual activities.
- Moderate (Grade 2): Sign or symptom, which may be ameliorated by simple therapeutic measures, may interfere with usual activity.
- Severe (Grade 3): Sign or symptom that is intense or debilitating and that interferes with usual activities and/or requires hospitalization. Recovery is usually aided by therapeutic measures and the discontinuation of the study product may be required.
- Life-threatening or disabling (Grade 4): Sign or symptom that is Life-threatening or disabling.
- Death (Grade 5): Death related to AE

## 9.3. CAUSALITY ASSESSMENT OF ADVERSE EVENTS (AEs)

All AEs will be evaluated by the investigator and assigned an estimated relationship to the RZL-012 investigational product. The terms "probable", "possible", "unlikely", or "unrelated" refer to the association with the use of the investigational product, as defined below in Table 4.

Medical judgment should be used to determine the relationship, considering all relevant factors, including pattern of reaction, temporal relationship, confounding factors such as concomitant medication, concomitant diseases and relevant history.

Assessment of causal relationship should be recorded directly in subjects CRF.

Definition of AEs causality is specified in the table below (Table 4).

**Table 4: Definition of Causality** 

TERM	DEFINITION	CLARIFICATION
Unrelated	This category applies to those AEs which, after careful consideration, are clearly due to extraneous causes (disease, environment, etc.)	
Unlikely Related	In general, this category can be considered applicable to those AEs, which after careful medical consideration at the time they are evaluated, are judged to be unrelated to the study procedures/investigational product.	
 
An AE may be considered unlikely related if or when (must have two):
 
It does not follow a reasonable temporal sequence from the study procedures/administration of the investigational product.
 
It could readily have been produced by the subject's clinical state, environmental or toxic factors, or other modes of therapy administered to the subject.
 
It does not follow a known pattern of response to the study procedures/investigational product.
 

Possibly Related		An AE may be considered possibly related if or when (at least two of the following):

26 May 2017 63 CONFIDENTIAL

TERM	DEFINITION	CLARIFICATION
	evaluated, a connection with the study procedures/investigational product administration appears unlikely but cannot be ruled out with certainty.	
 
It follows a reasonable temporal sequence from study procedures/administration of the investigational product.
 
A causal relationship to the experimental treatment cannot necessarily be reasonably excluded and an alternative explanation (e.g., concomitant investigational product or concomitant disease) cannot be reasonably suggested as causing the treatment emergent AE
 
It follows a known pattern of response to the study procedures/ investigational product.
 

Probably Related	This category applies to those AEs which, after careful medical consideration at the time they are evaluated, are felt with a high degree of certainty to be related to the study procedures/investigational product.	
 
An AE may be considered probably related if or when (at least three of the following):
 
It follows a reasonable temporal sequence from study procedures/administration of the investigational product.
 
It could not be reasonably explained by the known characteristics of the subject's clinical state, environmental or toxic factors, or other modes of therapy administered to the subject.
 
It disappears or decreases on cessation or reduction in dose. There are important exceptions when an adverse event does not disappear upon discontinuation of the investigational product, yet investigational product-relatedness clearly exists.
 
It follows a known pattern of response to the study procedures/investigational product.
 

Definitely Related	This category applies to those AEs which, after careful medical consideration at the time they are evaluated, are felt with definite certainty to be related to the study procedures/investigational product.	An AE may be considered definitely related if or when all of the following apply:  It follows a reasonable temporal sequence from study procedures/administration of the investigational product.  It could not be reasonably explained by the known characteristics of the subject's clinical state, environmental or toxic factors, or other modes of therapy administered to the subject.  It disappears or decreases on cessation or reduction in dose. There are important exceptions when an adverse event does not disappear upon discontinuation of the investigational product, yet investigational product-relatedness clearly exists.  It follows a known pattern of response to the study procedures/investigational product.

\*In this protocol Unlikely is deemed as Unrelated.

## 9.4. UNEXPECTEDNESS OF ADVERSE DRUG REACTIONS

An ADR is considered unexpected when its nature or severity is not consistent with the applicable product information (i.e., RZL-012 Investigator's Brochure).

### 9.5. ADVERSE EVENT REPORTING AND MONITORING REQUIREMENTS

#### **9.5.1.** General

All adverse events, serious and non-serious, will be fully documented in both source documents and CRFs as described in Section 6.1.16, and each AE will be assessed in light of its clinical significance. For each adverse event, the investigator will provide the onset, end, intensity, treatment required, outcome, seriousness and action taken with the investigational drug. The investigator will determine the relationship to the investigational drug, i.e., causality assessment, for each AE.

Any AE occurring prior to initiation of first dose, after initiation of the first dose and or during any point throughout the study should be recorded on the Adverse Event page of the CRF. All adverse events occurring until subject is terminated from the study (28 days after the injection of RZL-012 and in the highest dose cohort until 6 months from injection of RZL-012), should be captured in the CRF. AEs should be recorded in the CRF using the medical terminology found in the source documentation. Whenever possible, diagnoses should be given when signs and symptoms are due to a common etiology.

Occurrence of any Grade 4 and Grade 3 or 4 ADR must warrant clinical evaluation by the treating investigator and reported to the Sponsor within 7 calendar days.

ADRs graded > 1 will be followed-up until resolution, or for a maximal duration of 6 months after RZL-012 injection, whichever occurs first.

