#### 6.1.16. Adverse Events

The information obtained during weekly subjects questioning, review of subject's compliance record, physical examinations, vital signs measurements, blood testing, and by any other means will be evaluated in light of baseline medical data and thus provide the basis for adverse events identification and grading.

The trial will proceed within a cohort and from one cohort to the next as long as no more than one subject experiences intolerable side effects and based on the decision made by a DSMB. Proceeding from one cohort to the next will be based on the decision made after reviewing all safety data collected by Day 14 within  $2 \pm 1d$  of the last dosed subject in each cohort. The DSMB will be comprised of two independent MDs expert in early phase clinical trials.

The adverse events reported during the trial will be graded (see Section 9), documented, and assessed in light of their clinical significance and relation to investigational product. In addition, the following information regarding the AE must be obtained: AE description, start date, end date (if applicable) or ongoing, severity, seriousness, relationship to study drug, outcome (e.g., resolved / unresolved), and action taken (e.g., concomitant medication). The sponsor or the sponsor representative will provide information regarding SAE expectedness based on data included in the IB. Adverse event monitoring will be conducted throughout subject's participation up to 28 days after injection. For the 1st and 2nd cohort subjects will be additionally followed for AE at visit Day 56. If Draize score is 0 for erythema and edema, subjects of these cohorts and subjects of the 3rd and 4ths who terminate the study before visit Day 112, will be followed at Day 84 and Day 112 by phone-call questioning. For the 3rd and 4th cohort (or the highest dose achieved) adverse events will be recorded after Day 28 every 28 days if subject did not terminate participation in the study.

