Thermal Imaging - in subjects from the 3 rd and 4 th cohorts (or in cohort 2 if 2 subjects experience intolerable side effects within the 3 rd cohort)		Every 28 days. On Days 56, 84, 112, 140, 168
MRI	At screening Day 2 and at Day 28	
MRI - in subjects from the 2 nd cohort		On Day 56
MRI - in subjects from the 3 rd and 4 th cohorts (or in cohort 2 if 2 subjects experience intolerable side effects within the 3 rd cohort)		Every 28 days. On Days 56, 84, 112, 140, 168
Biopsy – in subjects from the 3 rd cohort or in cohort 2 if 2 subjects experience intolerable side effects within the 3 rd cohort		On Day 56
AE Assessment	At Days 1, 3, 7, 14, 21, 28	Every 28 days
Cohorts 1 and 2: AE Assessment by phone	Days 84 and 112	

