### 10. STATISTICAL CONSIDERATIONS

### 10.1. STUDY DESIGN AND OBJECTIVE

The purpose of this phase 2a study is to find the tolerated dose that provides the largest thermogenic effect.

The study is designed as a randomized, double-blind, two-arm clinical trial. Eligible subjects will be randomized to receive either RZL-012 or placebo (vehicle). In this feasibility study, different parameters of efficacy assessment will be measured in the all dose groups for a maximum period of up to 6 months. Subject follow-up for safety will be up to 112 days after treatment administration for the two lower doses cohorts and up to 168 days after treatment administration for the last two highest dose cohorts or up to 112 as the first 2 cohorts in case of termination before visit Day 112.

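### Section 9.5.1 gives conflicting end points for entering adverse events in the CRF: one reading stops at Day 28 below the highest dose, although contacts are planned to Day 112 or 168

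*Protocol*

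**What the plan says.** Protocol section 9.5.1 makes three statements about CRF entry of AEs:

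- All AEs "will be fully documented in both source documents and CRFs as described in Section 6.1.16".
- Any AE before the first dose, after it, or "during any point throughout the study should be recorded on the Adverse Event page of the CRF". This carries no day or cohort limit.
- AEs up to the subject's termination are to be captured, with termination explained in brackets as "28 days after the injection of RZL-012 and in the highest dose cohort until 6 months from injection of RZL-012".

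Section 6.1.16, to which the first statement points, opens with a similar limit: "Adverse event monitoring will be conducted throughout subject's participation up to 28 days after injection". Its next sentences extend that limit. Cohorts 1–2 have an AE assessment at Day 56. Those with a Draize score of 0, and cohort 3–4 subjects who leave before Day 112, "will be followed at Day 84 and Day 112 by phone-call questioning". For cohorts 3 and 4, or the highest dose reached, "adverse events will be recorded after Day 28 every 28 days if subject did not terminate participation in the study".

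Other places support the longer period. Section 10.1 states: "Subject follow-up for safety will be up to 112 days after treatment administration for the two lower doses cohorts". It gives up to 168 days for the other two cohorts, or 112 for subjects who terminate before then. Table 2 has the row "Cohorts 1 and 2: AE Assessment by phone" at Days 84 and 112, and Appendix I agrees.

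The primary safety endpoint (10.2.1) covers intolerable side effects and AEs of any kind. Section 10.5.4 reports both incidences by treatment and by cohort with exact 95% intervals. Neither 10.5.4 nor the safety analysis in SAP section 5.8 states a time window for counting AEs.

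**The concern.** With no window in the analysis, the any-AE incidence counts whatever has reached the database. The end of CRF entry therefore becomes, in effect, part of the endpoint definition, and the protocol gives it two values.

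The bracket also treats cohorts differently. Read literally, the highest-dose cohort contributes up to six months of AEs and the others contribute 28 days. Section 10.1 says the study is meant to find the tolerated dose with the largest effect. Unequal capture would make lower doses look safer beside the top dose for a reason unrelated to the drug.

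Late local events are plausible on the protocol's own account. Section 7.2 reports inflammation in adjacent fat still present at 56 days in animals, and section 6.1.10 provides for Draize scores above 0 at Day 56. The cohort 3 biopsy on Day 56 and its seven days of follow-up (section 6.1.14) also fall wholly after Day 28.

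**Working it through.** **Inputs.** Four cohorts of 6 active and 2 placebo subjects (synopsis): 4 × (6 + 2) = 32. Bracket: Day 28, or six months in the highest-dose cohort (9.5.1). Planned safety follow-up: 112 days in cohorts 1–2 and up to 168 days in cohorts 3–4 (10.1).

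**Reproducing the planned follow-up.** In cohorts 1–2 the contacts after Day 28 are Days 56, 84 and 112, so the last is Day 112. In cohorts 3–4 they are Days 56, 84, 112, 140 and 168, so the last is Day 168. Both agree with section 10.1.

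**Days uncovered per subject if the bracket alone governed** (planned end minus 28):

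- Cohorts 1–2: 112 − 28 = 84; 84/112 = 75%.
- Cohort 3, if not counted as the highest-dose cohort: 168 − 28 = 140; 140/168 = 83%.
- Cohort 4: none.

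**Share of planned subject-days**, assuming 8 subjects per cohort and full follow-up:

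- Denominator: 16 × 112 + 16 × 168 = 1,792 + 2,688 = 4,480.
- Bracket read as covering cohorts 3 and 4: 16 × 84 = 1,344; 1,344/4,480 = 30%; 16 subjects.
- Bracket read as cohort 4 alone: 1,344 + 8 × 140 = 2,464; 2,464/4,480 = 55%; 24 subjects.
- As the previous line, but with the three biopsied subjects followed to Day 112: (1,344 + 5 × 140 + 3 × 84) / (1,792 + 5 × 168 + 3 × 112 + 8 × 168) = 2,296/4,312 = 53%.
- Unlimited sentence of 9.5.1 together with the extensions in 6.1.16: 0 days uncovered.

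**Effect of one missed subject on the protocol's own analysis** (exact 95% intervals). This applies to a subject whose only AE is late.

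| Group | Event missed | Event captured |
|---|---|---|
| One active cohort | 0/6 = 0% (0 to 45.9%) | 1/6 = 16.7% (0.4 to 64.1%) |
| All active | 0/24 = 0% (0 to 14.2%) | 1/24 = 4.2% (0.1 to 21.1%) |

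**The case against.** A reader might infer that 9.5.1 requires AE capture only to Day 28 outside the top dose, so that late events in cohorts 1–3, including biopsy complications, are discarded. The documents do not support that. The sentence before the bracket has no day limit, and the section refers CRF documentation to 6.1.16, which plans AE contacts after Day 28 in every cohort. Read with its neighbours, the bracket is a careless explanation of when a subject leaves the study.

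Three further points stand:

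- **The gravest events are protected.** Section 9.5.2 sets no end date for serious AEs and requires their entry on CRF forms. Section 9.5.1 requires Grade 3 or 4 drug reactions to be reported to the sponsor without a day limit, and reactions above Grade 1 to be followed for up to six months. Intolerable side effects are essentially related events of Grade 3 or more (3.3.2), so that part of the endpoint is largely covered.
- **Cohort 3 is uncertain.** The bracket uses the singular, but sections 6.1.10 and 6.1.16 pair cohorts 3 and 4, and 10.1 speaks of the two highest together. If the bracket means both, cohort 3 and its biopsies are inside the window.
- **Incidence counts subjects.** A late AE in someone who already had an early one does not change the any-AE count, though it can change the tables by preferred term and severity.

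This does not remove the contradiction. The bracket supplies an explicit end of study against which a site can read the unlimited sentence. Section 6.1.16 itself opens with 28 days. It says late AEs are recorded in cohorts 3–4 but only that subjects are followed in cohorts 1–2, so the cross-reference does not clearly settle CRF entry for those 16 subjects.

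**Conclusion.** Section 9.5.1 contradicts itself and the schedule. The consequence is a risk that depends on which sentence a site follows; it is not a certain loss of data. What is exposed is late non-serious AEs in the lower-dose cohorts, and through them the any-AE incidence and its comparison by dose.

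The uncovered share runs from 0, through 30% of planned subject-days (cohorts 1–2 only), to at most 55% (cohorts 1–3). The upper figures assume that the bracket alone governs, that cohorts are full and that follow-up is complete. The 55% further assumes that cohort 4 opens and that the bracket means cohort 4 alone. Follow-up to Day 168 is itself a maximum.

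It would go too far to say that biopsy complications drop out of the primary endpoint. They are AEs under section 9.1.1. However, the endpoint refers to AEs of the injection, so whether they count is unclear whatever the window.

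The SAP cites protocol version 1.4 of 4 March 2018. The protocol text available is numbered 001.2 and dated 26 May 2017, so whether the bracket survived cannot be checked here. The correction is worth making because it touches a primary endpoint and costs almost nothing.

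**What to change.** Replace the bracket in 9.5.1 and the opening window in 6.1.16 with one rule: all AEs are entered in the CRF until the subject's last planned safety contact under sections 6.1.16 and 10.1. On the existing schedule that is:

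- Day 112 in cohorts 1–2;
- up to Day 168 in cohorts 3–4;
- the Day 112 call for cohort 3–4 subjects who terminate earlier, including those biopsied.

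Capture for biopsied subjects should not end with the seven-day post-biopsy follow-up, at about Day 63 (56 + 7). The synopsis and sections 6.1.16 and 10.1 keep early leavers of cohorts 3–4 in safety follow-up to Day 112, so the earlier stop would open a new gap.

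State the same window in the SAP safety analysis, and say there how biopsy-related AEs are counted. Confirm first whether the current protocol version still carries the bracket.

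The cost is a sentence in each of two protocol sections, a matching line in the CRF completion guide and a short SAP addition. No new visits or calls are needed.

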#### 3.3. DOSING

#### 3.3.1. Dosing Regimen

The dosing regimen will be a single dose treatment injection of RZL-012 in multiple sites.

The first 6 subjects randomly assigned to the RZL-012 treatment group (cohort 1) will initiate at the dose of 40 mg RZL-012 (approximately 1/6.25th the NOAEL as determined in the GLP toxicology study) and 2 more subjects will be given placebo (vehicle).

If no more than 1 subject experiences intolerable side effects within the 1st cohort, 14 days following the injection of the last dosed subject, an additional 6 subjects will receive a dose of 80 mg RZL-012 (approximately 1/3.125th of the NOAEL) and 2 more subjects will be given placebo (vehicle).

If no more than 1 subject experiences intolerable side effects within the 2nd cohort, 14 days following the injection of the last dosed subject, an additional 6 subjects will receive a dose of 120 mg RZL-012 (approximately1/2.34th of the NOAEL) and 2 more subjects will be given placebo (vehicle).

If no more than 1 subject experiences intolerable side effects within the 3rd cohort, 14 days following the injection of the last dosed subject, according to schedule an additional cohort of 6 volunteers, as above, will receive 180 mg RZL-012 (1/1.39 of the NOAEL). Additional 2 subjects in the cohort will serve as control and will be injected placebo (vehicle).

Dosing of the first 3 subjects in each cohort will progress consecutively from one individual to the other at 7-day intervals. For additional precaution, the first 3 subjects will be forced randomization with 2 active and 1 control. This study design will allow the physicians to monitor safety in a single subject at each dose; nevertheless, the blindness will remain intact.

The next subjects in the cohort will be randomized to either active treatment or placebo in a ratio determined by the number of subjects targeted for each cohort. Dosing of the next subjects will be in couples and the last subjects will be in a triplet.

If 1 subject had already experienced intolerable side effects in a cohort, then enrollment will progress consecutively from one individual to the other at 7-day intervals until that cohort is complete.

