The trial will proceed within a cohort and from one cohort to the next as long as no more than one subject experiences intolerable side effects in the lower-dose cohort, and based on the decision made by a DSMB. The decision to proceed to the next cohort will be made after reviewing all safety data collected by Day 14 within  $2 \pm 1d$  of the last dosed subject in each cohort. The DSMB will be comprised of two independent medical doctors (MDs) expert in early phase clinical trials.

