#### 3.3.2. Intolerable Side Effect

Safety will be the principal primary endpoint of this study, as such if there are 2 intolerable and at least possibly related side effects observed in any dose cohort, that dose cohort will be stopped and only tolerable doses used for future subjects.

An intolerable side effect defined as any of the following treatment-related adverse drug reactions (ADRs):

- Any Grade 3 or greater event except for the following (For the following entities, a discussion will be held by the PI, DSMB and Sponsor to decide whether considered as an intolerable side effects):
  - o Flu-like symptoms and fever that responds to standard treatment within 72 hours
  - Localized edema and erythema
  - o Pruritus
  - o Pain
  - Skin/soft tissue inflammation
  - Fat Atrophy
  - o Liver enzymes abnormality

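### A non-serious Grade 3-4 drug reaction may reach the Sponsor up to 7 days later, as long as the interval between the first three doses, and no time limit or route is set for telling the DSMB within a cohort

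*Protocol*

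**What the plan says.** **Reporting.** Under Protocol 9.5.1 a Grade 3 or 4 drug reaction "must warrant clinical evaluation by the treating investigator and reported to the Sponsor within 7 calendar days". The start of that clock is not stated. Section 9.5.2 sets 24 hours from awareness, but for serious events only.

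**Dosing.** Section 3.3.1 states: "Dosing of the first 3 subjects in each cohort will progress consecutively from one individual to the other at 7-day intervals". For subjects 4 to 8 it adds: "Dosing of the next subjects will be in couples and the last subjects will be in a triplet". No interval is given for these groups. If one subject in the cohort has had intolerable side effects, "then enrollment will progress consecutively from one individual to the other at 7-day intervals until that cohort is complete". Two such events stop the dose level (3.3.2).

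**DSMB.** Section 3.3.1 says: "The trial will proceed within a cohort and from one cohort to the next as long as no more than one subject experiences" an effect of this kind. It makes progress depend on a DSMB decision as well. The Synopsis and 6.1.16 agree. Timing is given only for the step between cohorts: "Proceeding from one cohort to the next will be based on the decision made after reviewing all safety data collected by Day 14".

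**Classification.** Section 3.3.2 makes related Grade 3+ events intolerable, except for a list covering flu-like symptoms and fever, local edema and erythema, pruritus, pain, skin or soft-tissue inflammation, fat atrophy, liver enzymes and short-lived laboratory changes. For these, "a discussion will be held by the PI, DSMB and Sponsor to decide whether considered as an intolerable side effects". No deadline is set. The same section then introduces grading tables for pain, tenderness, erythema, induration and ALT/AST, and says that Grade 3 or above on those tables is intolerable.

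**The concern.** The stagger is there so that what happens to one subject can inform the decision to dose the next. A reporting limit as long as the stagger means that two of the three parties who classify a listed event, the Sponsor and the DSMB, need not have heard of it when the next syringe is filled. The DSMB is also meant to have a say in progress within the cohort, but nothing says when or how it learns of an event before the Day 14 review that closes the cohort.

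The classification matters because it drives dosing: one affected subject forces one-by-one dosing, and a second event stops the level. If the second event waits for a report that is not yet due, a subject could be dosed at a level that the protocol would have closed.

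**Working it through.** The plan gives no figure of its own here, so the check is a timeline.

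**Inputs.** Reporting limit of 7 calendar days (9.5.1) or 24 hours for serious events (9.5.2); doses to subjects 1, 2 and 3 on Days 0, 7 and 14 (3.3.1); adverse event checks on Days 1, 3, 7, 14, 21 and 28 (Table 2); 6 active and 2 placebo subjects per cohort, with 2 active and 1 placebo among the first three. Assumption: the clock starts on the day the event is found.

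**Step 1: is the report due before the next dose?** Due day = day found + limit; the next dose is on Day 7.

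| Found on day | Due, 7-day limit | Due, 24-hour limit |
|---|---|---|
| 0 | 0 + 7 = 7 | 0 + 1 = 1 |
| 1 | 1 + 7 = 8 | 1 + 1 = 2 |
| 3 | 3 + 7 = 10 | 3 + 1 = 4 |
| 6 | 6 + 7 = 13 | 6 + 1 = 7 |

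Under the 7-day limit, anything found on Days 1 to 6 is due on Days 8 to 13, after the next dose. Under 24 hours the Day 1 and Day 3 findings arrive in time. A Day 6 finding falls due on the dosing day itself, which is why a shorter deadline also needs a pre-dosing check.

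**Step 2: what does a late first event change?** After an event in subject 1 or 2, the slow-down rule allows one subject per 7 days. That is already the schedule for subjects 2 and 3. Doses given 1, doses allowed 1, difference 0.

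**Step 3: what does a late second event change?** Suppose one event is already classed as intolerable, so dosing is one by one at 7-day intervals. A second event found on Days 1 to 6 after a dose may be reported as late as Days 8 to 13. One further dose falls in that time (Day 7), and the one after (Day 14) does not. Doses given 1, doses allowed 0, difference 1.

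**Step 4: would that subject be on active drug?** Subjects 4 to 8 comprise 6 - 2 = 4 active and 2 - 1 = 1 placebo. If the second event is in an active subject of this group who is not the last, the other four are 3 active and 1 placebo, so the next is on active with probability 3/4. Within the first three, if subjects 1 and 2 are both active and both have events, subject 3 is on placebo.

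**Step 5: after subject 3.** A first event in subject 3 could be reported after the couple has been dosed together, where one-by-one dosing should apply. The protocol states no interval for the couples or the triplet, so no number of subjects can be derived.

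**The case against.** The strongest reply is that the Sponsor report is not what protects the next subject. The trial has one site (Synopsis), and the PI there sees the event. The slow-down rule is tied to a subject having experienced the effect, so it binds the PI at once. Seven days is an outer limit on paperwork and does not authorize dosing without the DSMB decision that the protocol requires. Serious events reach the Sponsor in 24 hours, and some Grade 4 events, such as hospitalization for pain, are serious by definition, so what remains is mainly non-serious Grade 3. If the table rule in 3.3.2 governs, Grade 3+ pain, tenderness, erythema, induration and ALT/AST are intolerable without discussion. That leaves fever and flu-like symptoms, pruritus, other skin inflammation, fat atrophy and short-lived laboratory changes.

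Most of this stands and makes the gap small. It does not close it. A PI who knows of a listed event still cannot classify it alone under 3.3.2, and the other two parties have no deadline for being told. The list and the table rule also pull in different directions for pain, erythema or edema, and liver enzymes, so which events need the joint decision is not settled. The 5-working-day limit for CRF entry (6.2) does not help: it is not a report to the Sponsor and can span 7 calendar days.

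Two stronger readings are tempting. A reader might infer that nothing prompts action within a cohort; the one-event slow-down, the two-event stop and the joint discussion are all event-based rules, so what is missing is the time limit and the route to the DSMB. A reader might also infer that the couple and the triplet could all be dosed before a report is due; that rests on a spacing the documents do not give.

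**Conclusion.** The point holds in a limited form. The 7-day limit equals the 7-day stagger, and no section says by when or by what route the DSMB is told of an event during a cohort, although it has a part in both within-cohort progress and the classification of listed events. The firm consequence is one more subject dosed at a level that should stop, and only if a second non-serious event is reported late and dosing goes ahead meanwhile. For a first event in subject 1 or 2 the effect is nil.

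This assumes that the clock runs from the day of finding and that the PI does not hold dosing on personal judgment. Faster reporting also has a limit: it cannot catch an event first seen after the next dose. The severe ALT rise in Phase 0 was seen 14 days after injection (1.2.4), beyond the 7-day interval. The change is worth making because it is cheap and bears on a dosing decision, not because a large number of subjects is exposed.

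**What to change.** In 9.5.1, require any Grade 3 or higher drug reaction, serious or not, to be reported to both the Sponsor and the DSMB within 24 hours of the site becoming aware. Add that, before each dosing day, the PI confirms that no such event in the cohort is unreported or still awaiting the joint classification in 3.3.2.

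The stopping rule should stay as it is. Counting every unclassified event as intolerable in the meantime would change that rule, which is a separate and debatable trade-off.

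The cost is a few lines of text and a little more reporting work at one site with 32 subjects; no visit or measurement is added. Dosing may occasionally be held for a short time while an event is classified. Some list items depend on time, such as "Flu-like symptoms and fever that responds to standard treatment within 72 hours" and laboratory changes that must last less than 7 days, so the wait could run to those limits unless the three parties decide sooner.
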